## **9.5. Safety Analyses**

### **9.5.1. Adverse Events**

A TEAE is either any AE reported for the first time or worsening of a pre-existing event after first dose of study drug. Analysis of AEs will be limited to TEAEs, but data listings will include all AEs, regardless of their timing to study drug administration. Adverse events will be tabulated by the MedDRA preferred term and system organ class. Severity of AEs will be based on the NCI CTCAE v4.03 ([NCI 2010](#)).

- The subset of AEs considered by the investigator to have a relationship to study drug will be considered to be treatment-related AEs. If the investigator does not specify the relationship of the AE to study drug, the AE will be considered treatment-related. The incidence of AEs and treatment-related AEs will be tabulated.

### **9.5.2. Clinical Laboratory Tests**

Laboratory test values outside the normal range will be assessed for severity based on the normal ranges for the clinical reference laboratory. The incidence of abnormal laboratory values and shift tables relative to baseline will be tabulated.

Laboratory data will be classified into CTC grades for AEs (CTCAE v4.03). The following summaries will be produced for the laboratory data:

- Number and percentage of subjects with worst postbaseline CTC grade (regardless of baseline value) will be summarized. Each subject will be counted only for the worst grade observed postbaseline.
- Shift tables using CTC grades to compare baseline with the worst postbaseline value will be produced with CTC grade.
- For laboratory parameters where CTC grades are not defined, shift tables to the worst postbaseline value will be produced using the low/normal/high classifications based on laboratory reference ranges.

### **9.5.3. Vital Signs**

Descriptive statistics and mean change from baseline will be determined for vital signs (blood pressure, pulse, respiratory rate, and body temperature) at time assessments noted ([Table 5](#)). Vital signs will be reviewed for clinically notable abnormalities based on established age range-adjusted standards as defined in the Statistical Analysis Plan.

### **9.5.4. Electrocardiograms**

Electrocardiogram results will be reviewed for clinically notable abnormalities according to predefined criteria. Subjects exhibiting clinically notable ECG abnormalities will be listed. Adverse events will be reported for clinically notable abnormalities that are considered clinically significant in the judgment of the investigator.

[figure not shown]
## 9.6. Pharmacokinetic and Pharmacokinetic/Pharmacodynamic Analyses

The PK parameters of  $C_{max}$ ,  $T_{max}$ ,  $C_{min}$ ,  $AUC_{0-t}$  ( $AUC_{0-t}$  on Day 1), and  $Cl/F$  will be calculated from the blood plasma concentrations of itacitinib using standard noncompartmental (model-independent) PK methods. Pharmacokinetic calculations will be performed using commercial software such as WinNonlin® (Pharsight Corporation, Mountain View, CA). Nominal times will be used for in-stream data analyses. In Phase 1, PK bridging between pediatric and adult GVHD patients will be based on steady-state AUC. The totality of safety data will be considered for intrasubject dose modification, and in addition to safety, PK data will be used for intersubject dose modification for the study cohort and subsequent age specific cohorts. In the absence of any difference in safety between pediatric subjects in the first cohorts in Phase 1 and adult GVHD patients, PK data will be used to guide a potential dose modification in pediatric subjects enrolled in subsequent cohorts. Sixty-seven percent to 150% is the clinically insignificant range based on the variability of itacitinib PK. To trigger a dose reduction, the lower bound of the 90% CI of the GMR for exposure (AUC) would have to be greater than 1.5. To trigger a dose increase, the upper bound of the GMR 90% CI for exposure would have to be less than 0.67. The new dose will be determined via simulation with the target that median exposures for a given dose across the cohort should fall between the interquartile exposure range observed in adult GVHD patients. It should be noted that in adults, the PK sampling scheme included sampling at predose, 1 hour, 2 hours, and 4 to 8 hours (generally sampled close to 4 hours), and for comparison between adult and pediatric exposure, the pediatric data maybe modified to only include these timepoints in case the adult exposures are overestimated due to the sampling scheme.

A population PK model will be developed using nonlinear mixed-effects modeling. The initial structure of the model will be based on a population PK analysis in adults comprised of healthy volunteers and several patient populations including GVHD. Stepwise modelling will be performed using forward addition/backward elimination exploring various intrinsic and extrinsic factors that may affect PK, such as patient demographics, disease status, and concomitant medications. If clinically significant covariates are identified, simulation will be used for dose optimization. The following covariates will be evaluated: body weight, age, gender, race, ethnicity, concomitant administration of CYP3A inhibitors, concomitant administration of CYP3A inducers, renal function, hepatic function, and GVHD disease status (including affected organs and/or severity). Models will be evaluated using standard goodness-of-fit plots, successful convergence, typical ETA plots, magnitude of the random effects, plausibility of parameter estimates, and precision of the parameters estimates. Visual predictive checks and/or pcVPCs will also qualify the model. Bootstrap analysis will be performed to test model stability and determine precision of the PK parameter estimates. The VPC (or pcVPC) and bootstrap analyses will be stratified by age group. Additional details of this analysis will be provided in a separate data analysis plan.

The relationship between total exposure (AUC), as determined by modeling and simulation using individual posterior parameter estimates, and the primary efficacy endpoint ORR (as a binomial variable comprising nonresponders in one category and responders with CR, VGPR, and PR in the other category) will be explored graphically and quantitatively characterized using a logistic regression model whereby inclusion of total exposure as a predictor of response must be statistically significant at the  $p < 0.05$  level for inclusion. If total exposure is not significant in

the model, then the conclusion will be drawn that given the limited range of exposures, no relationship between PK and ORR was observed. The same analysis will be triggered for any DLT in  $\geq 25\%$  of the subjects, that is, the relationship between exposure and DLT will be explored and characterized.

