the 300 mg cohort. Most responses occurred within the first 14 days of treatment, and responses were durable. The median DOR was not reached in any of the dose cohorts; the median follow-up for DOR was 105 days (range: 29-827) for the 200 mg cohort and 185.5 days (range: 61-841) for the 300 mg cohort (IB). Pharmacokinetics of itacitinib were evaluated using plasma samples collected predose and at 1 hour, 2 hours, and 4 to 8 hours postdose on Study Days 1 and 7. Although intersubject variability was found to be high, PK exposure ( $C_{max}$  and AUC) was consistent with historical data, and a large overlap in steady-state exposure was observed between the 200 mg and 300 mg cohorts. The higher incidence of thrombocytopenia and DLT of thrombocytopenia in the 300 mg cohort, as well as similarities in PK and efficacy between dose groups, led to the identification of the 200 mg dose of itacitinib as the recommended phase 2 dose for future adult GVHD studies (Schroeder et al 2016). The treatment compliance rate and median duration of treatment were also higher in the 200 mg cohort than the 300 mg cohort. Day 28 ORR in standard-risk and high-risk aGVHD were identical between dose cohorts. All subjects with standard-risk aGVHD (MacMillan et al 2015) demonstrated response irrespective of treatment assignment, and 55.6% high-risk aGVHD subjects demonstrated response (200 mg dose cohort, n = 5, 55.6%; 300 mg cohort, n = 5, 55.6%; Incyte, data on file).

New treatments for the therapy of aGVHD after allo-HSCT are urgently needed globally including both adult and pediatric patient populations. Novel treatments with agents targeting the JAK-STAT pathway appear to decrease aGVHD while preserving GVT in murine models by targeting the IFN- $\gamma$  pathway in activated T cells responsible for aGVHD. The preclinical data with clinical proof-of-principle findings with ruxolitinib and itacitinib provide a strong rationale to further investigate itacitinib with corticosteroids in patients aGVHD.

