### **5.7.1. Withdrawal Criteria**

Subjects **must** be withdrawn from study treatment for the following reasons:

- The subject has experienced an unacceptable toxicity.
- Relapse of underlying malignancy or disorder.
- The subject is unable to tolerate itacitinib at a reduced dose specified for cohort.
- GVHD progression or lack of response. Requirement for additional systemic therapy, including corticosteroid doses greater than those used on Study Day 1, will qualify for GVHD progression.
- Further participation would be injurious to the subject's health or well-being, in the investigator's medical judgment.
- The subject becomes pregnant (may be applicable for Cohort 1).
- Consent is withdrawn.

- The study is terminated by the sponsor.
- The study is terminated by the local health authority, IRB, or IEC.

A subject **may** be withdrawn from study treatment as follows:

- If, during the course of the study, a subject is found not to have met eligibility criteria, then the medical monitor, in collaboration with the investigator, will determine whether the subject should be withdrawn from the study.
- If a subject is noncompliant with study procedures or study drug administration in the investigator's opinion, the sponsor should be consulted for instruction on handling the subject.

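### The exposure-response model for Day 28 ORR names AUC as its only predictor, so if baseline GVHD severity shifts AUC the slope is confounded, in either direction

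*Combined protocol and SAP*

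**What the plan says.** Section 9.6 has two model-based analyses, in consecutive paragraphs.

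- **Population PK model.** Covariates are searched stepwise, "exploring various intrinsic and extrinsic factors that may affect PK, such as patient demographics, disease status, and concomitant medications". The list to be evaluated includes "renal function, hepatic function, and GVHD disease status (including affected organs and/or severity").
- **Exposure-response model.** AUC, obtained by modelling and simulation from individual posterior parameters, is related to Day 28 ORR (responder or not). It is "quantitatively characterized using a logistic regression model whereby inclusion of total exposure as a predictor of response must be statistically significant" at p < 0.05. For the case where AUC misses that threshold, the sentence ends: "the model, then the conclusion will be drawn that given the limited range of exposures, no relationship between PK and ORR was observed".

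None of the PK covariates is named in the second model, and the text does not say whether the five cohorts are pooled. The pointer to a separate data analysis plan closes the population PK paragraph and so appears to refer to that model.

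On severity and response, Section 1.1 describes it as established that Grade III-IV disease responds less well to steroids, which are the background treatment here. Section 1.4.2 reports for the adult itacitinib study that all standard-risk subjects responded, while "55.6% high-risk aGVHD subjects demonstrated response". Inclusion criterion 3 admits Grades II to IV, so severity will vary within this trial.

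**The concern.** A variable that affects both exposure and outcome confounds the exposure-response slope. The documents give the severity-response link as an association and list the severity-AUC link as something to be tested. If the second link exists, an AUC-only logistic model attributes part of the severity effect to AUC.

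The error can run either way. If severe disease lowers AUC, children with low exposure respond less because they are sicker, and AUC looks beneficial when it is not. If severe disease raises AUC, the slope is pulled towards an inverse relation. A real benefit can then be masked, and the pre-written conclusion of no relationship would follow.

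The stake is interpretation of exposure and dose. Section 5.2.1 foresees that the Section 9.6 PK/PD analyses may recommend a dose change, although only after a substantial amendment is approved.

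**Working it through.** The plan states no power, effect size or sample size for this analysis, so there is no figure of its own to reproduce. The check asks how often an AUC-only model declares an AUC effect when there is none.

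**Inputs from the documents**
- Exposure CV 58% (Section 9.2): log SD = sqrt(ln(1 + 0.58²)) = 0.538.
- High-risk share: Section 1.4.2 gives 5 responders, 55.6%, in each dose group. 5/0.556 = 9 per group, so 18 of 29 treated adults (62%).
- Response in high-risk adults: 5/9 = 55.6%.
- About 150 children in total, about 30 per cohort (Section 4.3.1).

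**Assumptions**
- The ratio g of AUC, severe to less severe, is varied from 0.6 to 1.5. The documents give no estimate.
- Response, less severe versus severe: 95% versus 55.6%, or a weaker contrast of 75% versus 50%.
- The adult high-risk share applies to these children, and the test is two-sided.

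**Model.** log AUC = ln(g) × severe + Normal(0, 0.538²). Response depends on severity only. Firth logistic regression, Wald test at 5%, 2,000 trials per setting (Monte Carlo standard error at most 1.1 percentage points).

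**Hand check at g = 0.7, response 95% versus 55.6%**
- Responders: 0.6207 × 0.5556 + 0.3793 × 0.95 = 0.3448 + 0.3603 = 0.7052. Severe share among them: 0.3448/0.7052 = 0.489.
- Nonresponders: 0.6207 × 0.4444 + 0.3793 × 0.05 = 0.2759 + 0.0190 = 0.2948. Severe share: 0.2759/0.2948 = 0.936.
- Difference in mean log AUC, responders minus nonresponders: ln(0.7) × (0.489 − 0.936) = 0.159. Responders' geometric mean AUC is exp(0.159) = 1.17 times higher although AUC does nothing.
- The pooled within-group variance of log AUC is 0.315, so the slope is about 0.159/0.315 = 0.506. The odds ratio per AUC doubling is exp(0.506 × ln 2) = 1.42.

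**Simulated results, AUC-only model, n = 150 pooled**

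| g (assumed) | False AUC effect, 95% vs 55.6% | OR per doubling | False AUC effect, 75% vs 50% | OR per doubling |
|---|---|---|---|---|
| 0.6 | 54.2% | 1.58 | 21.9% | 1.28 |
| 0.7 | 32.8% | 1.42 | 14.3% | 1.21 |
| 0.8 | 16.2% | 1.25 | 8.6% | 1.14 |
| 0.9 | 6.8% | 1.12 | 5.1% | 1.07 |
| 1.0 | 4.3% | 1.00 | 4.5% | 1.00 |
| 1.25 | 14.4% | 0.80 | 8.5% | 0.89 |
| 1.5 | 38.7% | 0.68 | 16.2% | 0.81 |

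The simulated odds ratio at 0.7 agrees with the hand check. With the adult figure of 100% in the standard-risk group (4,000 trials), the rate is 48.4% at g = 0.67 and 49.8% at g = 1.5.

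**With severity in the model, n = 150.** The false AUC effect is 3.3% to 4.6% in all 14 settings, and the odds ratio is 0.99 to 1.01. Adding four cohort terms leaves the rate at 3.3% to 4.5%.

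**Single cohort, n = 30, AUC only.** Over the shifted settings the rate is 1.9% to 7.5%, because power is low. The slope is about as biased: for 95% versus 55.6%, the odds ratio is 1.56 at g = 0.6 and 0.69 at g = 1.5.

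For scale, Section 9.6 treats paediatric-to-adult exposure ratios of 67% to 150% as clinically unimportant. Severity shifts within that band (0.7 to 1.5 in the table) are enough to distort this test.

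**The case against.** **Severity may not affect AUC.** It is one of about ten covariates to be examined, and the plan does not call it a cause of PK variation. At g = 1.0 there is no confounding, and at 0.9 it is small. This stands, and it is why the size is given only as a range. One possible route is visible but conjectural: Section 1.5 reports about a 2-fold rise in exposure with posaconazole and recommends no dose adjustment. If, purely by assumption, 50% of severe and 10% of less severe children received it, the AUC ratio would be 2^(0.5 − 0.1) = 1.32. No passage says that sicker children receive more azoles.

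**The adult contrast is imperfect.** It compares risk groups rather than grades, in 29 treated adults with steroid-naive and steroid-refractory disease mixed. This stands. Section 1.1 is the direct statement on grade, and the weaker 75% versus 50% contrast is shown for this reason.

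**The analysis is exploratory.** Section 9.3 rules out formal tests. That limits the stakes, but Section 9.6 still sets a p-value rule and a conclusion that follows from it.

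**Other covariates are not excluded.** True: they are simply not named. The separate data analysis plan and the redacted text could not be read.

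**Two stronger readings are not supported.**
- A reader might infer reverse causation, because Section 5.7.1 requires withdrawal for "GVHD progression or lack of response" and withdrawn children would accumulate less exposure. But the AUC comes from individual PK parameters and is not said to accumulate over time on treatment. Phase 2 PK sampling is on Day 7 only. At most, the dosing interval needs stating.
- A reader might infer that the slope feeds PK bridging. Section 9.6 bases bridging on steady-state AUC and triggers dose changes from the 90% CI of the GMR; ORR is not an input.

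**Conclusion.** The point holds as a conditional one. As written, the model cannot separate an effect of AUC from an effect of severity if severity shifts AUC. With n = 150 pooled and no true AUC effect, the false-positive rate for g between 0.6 and 1.5 (other than 1.0) is about 7% to 54% under the stronger response contrast and 5% to 22% under the weaker one, against about 4% with no shift. At n = 30 the significance test seldom misfires, but the slope is still biased.

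These figures rest on assumed AUC ratios, assumed response rates and pooling that the plan does not state. The near-nominal rates after adjustment come from adjusting for the exact simulated factor. Baseline grade is an imperfect measure of risk, so some confounding could remain. The point does not touch the primary ORR estimate, the DLT rule or the GMR dose triggers. It is worth correcting because the remedy uses data already collected.

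**What to change.** In the exposure-response paragraph of Section 9.6, or in the analysis plan that details it:

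1. Keep baseline aGVHD grade (II versus III-IV, from the Day 1 assessment) in the logistic model whatever its p value.
2. State whether cohorts are pooled; if they are, include cohort as well.
3. State that the exposure is the model-based steady-state AUC at Day 7.
4. Report the adjusted odds ratio for AUC with its 95% CI as the main result and the AUC-only model as supportive. If the interval is wide, say that the data are inconclusive rather than that no relationship was observed.
5. Treat lower GI involvement at baseline as a sensitivity analysis, and use Firth estimation if nonresponders are few.

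**Cost.** Staging (Sections 7.3.2 and 7.6.1) and Day 7 PK (Section 7.7.1) are already collected, so no new data are needed. The price is precision. In the simulation with grade and cohort both added, the standard error of the log-AUC coefficient rises by between 6% (0.315 to 0.334) and 19% (0.321 to 0.383). Grade, AUC and four cohort terms make six slopes. Under the 95% versus 55.6% inputs there are 150 × 0.2948 = 44 nonresponders, about 7 per slope. This is why lower GI involvement is better kept out of the main model.

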### 9.2. Selection of Sample Size

With regard to safety and efficacy endpoints, sample size is based on the clinical feasibility and consideration. There is no hypothesis test. Phase 1 is a safety run-in in which 10 evaluable subjects will be assessed in each cohort for the safety, tolerability, and PK of itacitinib in combination with corticosteroids. For Phase 2, up to 30 subjects will be enrolled into each cohort (Cohort 1: 12 to < 18 years old, Cohort 2: 6 to < 12 years old, Cohort 3: 2 to < 6 years old, Cohort 4: weighing > 8 kg to < 2 years, and Cohort 5: 28 days old to weighing  $\leq$  8 kg). This includes the 10 subjects enrolled in Phase 1 for each cohort.

A total of 150 pediatric subjects will be enrolled into the study.

With regard to PK endpoints, approximately 30 subjects are sufficient to meet the criteria suggested by regulators regarding sample size in pediatric PK studies ([Wang et al 2012](#)). Given a CV% of 58% based on the preliminary PK data from study INCB39110-108 200 mg QD dose, 16 subjects are needed to achieve sufficient power based on the criteria proposed by Wang et al. Ten subjects will be included in the Phase 1 dose confirmation portion of the study. Although this sample size is lower than the needed sample size to meet the criteria proposed by Wang et al (N = 16), it is expected to yield meaningful PK information given the expected exposure variability and minimum magnitude of exposure difference observed in pediatric patients as compared with adults that would prompt consideration of a possible dose

modification (~50%); the PK data will be considered along with available clinical data, such as safety data. The sample size of the Phase 1 portion of the study was also chosen with the aim of minimizing the number of children exposed to itacitinib before any initial evaluation while obtaining a sufficient amount of data to guide decision-making.

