### **9.3. Level of Significance**

No formal statistical tests will be performed. All CIs will be 95%.

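### Section 9.6 ties a pre-written statement of no observed exposure-response relationship to p ≥ 0.05, with no slope or interval required; non-significance cannot carry that statement within one cohort, or for modest slopes when cohorts are pooled

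*Combined protocol and SAP*

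**What the plan says.** Section 9.6 of the protocol plans to relate AUC, "as determined by modeling and simulation using individual posterior parameter estimates", to Day 28 ORR as a binary outcome. The relationship "will be explored graphically and quantitatively characterized using a logistic regression model". A condition is attached: "inclusion of total exposure as a predictor of response must be statistically significant" at the p < 0.05 level. If the condition is not met, "then the conclusion will be drawn that given the limited range of exposures, no relationship between PK and ORR was observed".

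The section then says that the same analysis is triggered for any DLT seen in at least 25% of subjects. For DLT it says only that the relationship will be explored and characterized.

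The section does not say whether the regression pools the five cohorts or is run within each. It does not ask for the slope or its interval when p ≥ 0.05, and it names no smallest slope of interest. Section 9.3 says "No formal statistical tests will be performed" and sets all confidence intervals at 95%.

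**The concern.** A p value above 0.05 may mean that the slope is small, or that there were too few subjects or too little spread in exposure to estimate it. The interval separates these cases, and the plan does not ask for it. The prescribed sentence points to one cause, the exposure range, and leaves out the other, the number of subjects.

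What is at stake is what the trial reports about exposure and response. Section 1.4.3 rests the bridging approach on the expectation that similar exposures give similar effect. A slope with its interval would be direct pediatric evidence on how response varies with exposure. Under the rule, that evidence can be replaced by a fixed sentence when the data are least informative.

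**Working it through.** The plan gives no power, effect size or sample size for this analysis, so it has no figure to reproduce.

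**Inputs from the protocol**
- Exposure variability: "Given a CV% of 58% based on the preliminary PK data from study INCB39110-108 200 mg QD dose" (Section 9.2).
- Cohort size: "For Phase 2, up to 30 subjects will be enrolled into each cohort" (Section 9.2), so 5 × 30 = 150 in total.
- Possible shortfall: Section 4.3.1 says Cohorts 4 and 5 may not fill. Cohorts 1–3 alone give 3 × 30 = 90.
- Adult first-line Day 28 ORR: 83.3% at 200 mg and 66.7% at 300 mg (Section 1.4.2).

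**Assumptions**
- AUC is log-normal and the test is two-sided at 0.05.
- ORR lies between 50% and 83.3%. The plan assumes no pediatric ORR.
- Odds ratios (OR) per doubling of AUC are 1.5, 2 and 3. The plan names no target slope.
- N = 90 is an assumed low case for the pooled set.

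**Step 1. Spread of exposure.** SD of ln(AUC) = √ln(1 + 0.58²) = 0.538.

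**Step 2. Power.** With p the ORR, the slope per SD is b = (ln OR / ln 2) × 0.538, and power ≈ Φ(√(N·p(1−p)) × b − 1.96).

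Example with N = 150, p = 0.75 and OR 2: √(150 × 0.1875) = 5.303; 5.303 × 0.538 − 1.96 = 0.90; Φ(0.90) ≈ 81%.

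The ranges below run from ORR 83.3% (low power) to 50% (high power):

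| OR per doubling of AUC | N = 30 | N = 90 | N = 150 |
|---|---|---|---|
| 1.5 | 9–14% | 20–32% | 30–49% |
| 2 | 19–31% | 48–72% | 69–91% |
| 3 | 41–65% | 86–98% | 97% or more |

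For scale, at an ORR of 75%, OR 2 per doubling means response of about 57% at the 5th exposure percentile and 89% at the 95th.

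**Step 3. Simulation check.** With 3,000 runs per case, OR 2 and ORR 75%, likelihood-ratio / Wald power is 27% / 17% at N = 30, 58% / 55% at N = 90 and 79% / 77% at N = 150. The formula gives 25%, 60% and 81%. For OR 1.5 at N = 150, simulated likelihood-ratio power is 30–49% over the same ORR range, matching the formula.

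**Step 4. What the interval would show.** SE of ln(OR per doubling) = ln 2 / (0.538 × √(N·p(1−p))). Take an estimate of exactly 1.0 and p = 0.75:
- N = 30: SE 0.543, 95% CI 0.35–2.90.
- N = 90: SE 0.313, 95% CI 0.54–1.85.
- N = 150: SE 0.243, 95% CI 0.62–1.61.

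A flat result in one cohort would not exclude a near three-fold change in odds per doubling. Pooled over 150 it would exclude a doubling of the odds but not a 1.5-fold change.

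**Step 5. Sensitivity (OR 2, ORR 75%; N = 30 / 90 / 150).** CV 40%: 15% / 35% / 53%. CV 80%: 39% / 82% / 96%. If the posterior AUC estimates had a reliability of 0.7 (assumed), simulated likelihood-ratio power at CV 58% is 18% / 42% / 62%.

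**The case against.** The other side has several fair points.

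- **Sample size.** A reader might infer that a strong relationship would usually be missed. At the planned total the figures do not support that: with 150 subjects, OR 2 is found 69–91% of the time and OR 3 at least 97%. AUC comes from one population PK model with age and weight among its covariates, which points towards pooling. The inference fits a cohort-level analysis, where OR 2 is missed about 70–80% of the time. The section does not settle which is meant, and ORR itself is summarized by cohort (Section 9.4.1).
- **Wording.** The sentence reports what was observed and is hedged by exposure range. It does not assert that no relationship exists. The hedge is also partly right, because a narrower range lowers power (CV 40% in Step 5). It remains incomplete, because the number of subjects matters too.
- **Reporting.** The section promises graphs and a quantitative characterization, and nothing forbids reporting the slope. The criticism is that reporting is not required when p ≥ 0.05.
- **Section 9.3.** It is tempting to call the p < 0.05 rule a flat contradiction. It can be read as a predictor-inclusion criterion in exploratory modelling. Section 9.3 is worded broadly enough that one clarifying sentence is worthwhile, and no confirmatory claim depends on it.
- **DLT.** A reader might carry the fixed conclusion over to DLT. That sentence names ORR only.
- **Use of the result.** A reader might infer that it would be used to defend dosing across ages. No section says so. The PK triggers for changing a cohort's dose are the 90% CI limits of the geometric mean ratio against 0.67 and 1.5, and they do not use this regression.

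These points narrow the concern but leave the rule itself: a conclusion fixed in advance by a p value, with no interval required beside it.

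**Conclusion.** The point holds in a limited form. A non-significant AUC term cannot support a statement of no relationship within a cohort of 30, where power for OR 2 per doubling is 19–31% and a null estimate would carry a 95% CI of about 0.35–2.90. Pooled over 150, it can count against a doubling of the odds (null-estimate CI 0.62–1.61) but not against a modest slope, since power for OR 1.5 is 30–49%. With 90 subjects the position is intermediate.

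These sizes rest on an adult CV from one dose level, an assumed ORR range and assumed odds ratios. Wider exposure would raise power, and noisy posterior AUC estimates would lower it. The defect in the rule does not depend on the exact figures. This is a reporting weakness in an exploratory analysis and does not affect the primary ORR analysis.

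**What to change.** In Section 9.6 and the analysis plan:

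1. Fit the logistic model on log AUC in all PK-evaluable subjects, pooled across cohorts, and say so.
2. Whatever the p value, report the odds ratio per doubling of AUC with its 95% CI, and the predicted ORR at the 10th, 50th and 90th AUC percentiles.
3. Delete the p < 0.05 inclusion gate and the pre-written conclusion.
4. If the DLT exposure analysis is triggered, report it the same way.
5. Add a sentence to Section 9.3 saying that exposure-response modelling is exploratory estimation.

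The cost is a wording change to the protocol and the analysis plan, with no new data or subjects. The drawback is a less definite statement when the interval is wide.
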